Cycle 1:

Ublituximab			Umbralisib	Acalabrutinib
Day 1	Day 2	Day 8 & 15	Daily	Every 12 hours
150 mg	750 mg	900 mg	800 mg	previously tolerated dose

[figure not shown]
Cycles 2 through 6:

Ublituximab	Umbralisib	Acalabrutinib
Day 1	Daily	Every 12 hours
900 mg	800 mg	previously tolerated dose

Cycles 7-24:

Ublituximab	Umbralisib	Acalabrutinib
Day 1 of Cycles 9, 12, 15, 18, 21 and 24	Daily	Every 12 hours
900 mg	800 mg	previously tolerated dose

Study Schema - Re-Treatment

*Progression Of Disease (PD) – Defined per the iwCLL Criteria (Hallek 2018)

U2 – ublituximab and umbralisib; IB – ibrutinib; ACALA – Acalabrutinib; VEN – venetoclax; MRD – minimal residual disease; EOS – end of study

Retreatment will start with 2 cycles of single agent treatment with ibrutinib, acalabrutinib or venetoclax per the subject's history on study. Umbralisib and ublituximab will be started in Cycle 3 of re-treatment. Subjects will again be evaluated with serial peripheral blood MRD analysis. If subjects achieve U-MRD status in the peripheral blood, MRD will again be assessed by peripheral blood 4 weeks later to confirm U-MRD. Retreatment will continue until the occurrence of confirmed U-MRD response in the peripheral blood, completion of 26 cycles (24 cycles of triplet therapy), definitive disease progression, unacceptable toxicity, or withdrawal from the study due to investigator decision or other reasons. Subjects who discontinue study treatment and have not progressed will continue to be followed for disease progression.

Re-treatment schedule as follows:

Cohort A: Ublituximab and Umbralisib with Ibrutinib

Cycles 1 and 2:

Ibrutinib				
Daily				
Daily at previously tolerated dose. Investigator discretion may be used to start subjects at a higher dose than last tolerated (maximum dose 420mg daily).				

Cycle 3:

Ublituximab			Ibrutinib	Umbralisib
Day 1	Day 2	Day 8 & 15	Daily	Daily
150 mg	750 mg	900 mg	At appropriate dose based on initial protocol treatment	Previously tolerated dose. Investigator discretion may be used to start subjects at a higher dose than last tolerated (maximum dose 800mg daily).

Cycles 4 through 8:

Ublituximab	Ibrutinib	Umbralisib
Day 1	Daily	Daily
900mg	At appropriate dose based on previous Cycle	At appropriate dose based on previous Cycle

Cycle 9 through Cycle 26:

Ublituximab	Ibrutinib	Umbralisib
Day 1 of Cycle 11, 14, 17, 20, 23 & 26	Daily	Daily
900 mg	At appropriate dose based on previous Cycle	At appropriate dose based on previous Cycle

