Cohort C: Ublituximab and Umbralisib with Acalabrutinib																				
Cycle 1:																				

  
 Ublituximab	Umbralisib	Acalabrutinib	
 
 Day 1	Day 2	Day 8 & 15	Daily	Every 12 hours	
   
 150 mg	750 mg	900 mg	800 mg	previously tolerated dose	
  
						Ublituximab		Umbralisib	Acalabrutinib		Day 1	Day 2	Day 8 & 15	Daily	Every 12 hours	150 mg	750 mg	900 mg	800 mg	previously tolerated dose
Ublituximab		Umbralisib	Acalabrutinib																	
Day 1	Day 2	Day 8 & 15	Daily	Every 12 hours																
150 mg	750 mg	900 mg	800 mg	previously tolerated dose																
Cycles 2 through 6:																				

  
 Ublituximab	Umbralisib	Acalabrutinib	
   
 Day 1	Daily	Every 12 hours	
 
 900 mg	800 mg	previously tolerated dose	
  
						Ublituximab	Umbralisib	Acalabrutinib	Day 1	Daily	Every 12 hours	900 mg	800 mg	previously tolerated dose						
Ublituximab	Umbralisib	Acalabrutinib																		
Day 1	Daily	Every 12 hours																		
900 mg	800 mg	previously tolerated dose																		
Cycles 7-24:																				

  
 Ublituximab	Umbralisib	Acalabrutinib	
   
 Day 1 of Cycles 9, 12, 15, 18, 21 and 24	Daily	Every 12 hours	
 
 900 mg	800 mg	previously tolerated dose	
  
						Ublituximab	Umbralisib	Acalabrutinib	Day 1 of Cycles 9, 12, 15, 18, 21 and 24	Daily	Every 12 hours	900 mg	800 mg	previously tolerated dose						
Ublituximab	Umbralisib	Acalabrutinib																		
Day 1 of Cycles 9, 12, 15, 18, 21 and 24	Daily	Every 12 hours																		
900 mg	800 mg	previously tolerated dose																		
Study Drugs	Ublituximab is a recombinant chimeric monoclonal antibody against the CD20 antigen, available as a 25 mg/mL concentrate for solution for infusion, supplied by TG Therapeutics, Inc.																			

Umbralisib is a highly specific and orally available dual inhibitor PI3K delta (δ) and CK-1 epsilon available in 200 mg tablets, supplied by TG Therapeutics, Inc.

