5.4 RETREATMENT PHASE

Study Schema for Re-Treatment

*Progression Of Disease (PD) – Defined per the iwCLL Criteria (Hallek 2018)
U2 – ublituximab and umbralisib; IB – ibrutinib; ACALA – Acalabrutinib; VEN – venetoclax; MRD – minimal residual disease; EOS – end of study

Subject on treatment-free observation who subsequently develop clinical progression requiring treatment per iwCLL criteria (Hallek, et al., 2018) after 6 months of treatment-free observation will be retreated with the triple combination regimen that was previously received. Subjects who progress within 6 months of treatment-free observation discontinue from the study.

For subjects enrolled in Cohort A, retreatment will consist of 2 cycles of ibrutinib followed by treatment with ublituximab and umbralisib with ibrutinib cycles 3 through 26 of retreatment. The previously tolerated ibrutinib dose should be considered but is at investigator discretion (maximum dose 420mg daily).

For subjects enrolled in Cohort B, venetoclax should be initiated per the package insert. The target ramp-up dose should be considered based on the previously tolerated dose but is at investigator discretion (maximum dose 400mg daily). Retreatment will consist of 2 cycles of venetoclax followed by treatment with ublituximab and umbralisib with venetoclax cycles 3 through 26.

For subjects enrolled in Cohort C, retreatment will consist of 2 cycles of acalabrutinib followed by treatment with ublituximab and umbralisib and acalabrutinib cycles 3 through 26 of retreatment. The previously tolerated acalabrutinib dose should be considered but is at the investigator discretion.

Clinical response and U-MRD rate will be studied upon retreatment. If subjects achieve U-MRD status in the peripheral blood, MRD will be assessed by peripheral blood 4 weeks later to confirm U-MRD. Retreatment will continue until the occurrence of confirmed U-MRD response in the peripheral blood, completion of 26 cycles (24 cycles of triplet therapy), UTX-TGR-208

Version 2.0 Dated: 30 July 2020

definitive disease progression, unacceptable toxicity, or withdrawal from the study due to investigator decision or other reasons. Subjects who discontinue study treatment and have not progressed will continue to be followed for disease progression.

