⁹ Serum Virology to include HBsAg, HBC antibody, HCV antibody, CMV IgG and CMV IgM or CMV by PCR. If HBC antibody is positive, the subject must be evaluated for the presence of HBV DNA by PCR - See Appendix D. If the subject is CMV IgG or CMV IgM positive, the subject must be evaluated for the presence of CMV DNA by PCR.

¹⁰ CMV surveillance by PCR every 3 cycles while receiving study treatment. In addition, a final CMV test by PCR should be done upon treatment discontinuation if not already done within previous 3 months.

¹¹ For retreatment, MRD analysis should be done within 30 days of restarting therapy in peripheral blood (PB) then performed Cycles 6, 8, 11, 14, 17, 20, 23, and 26. If U-MRD in PB during retreatment repeat approximately 4 weeks later. If U-MRD confirmed approximately 4 weeks later, discontinue treatment and follow for progression and survival for 24 months.

¹³ For women of childbearing potential: Serum pregnancy test within 3 days prior to Cycle 1/Day 1; Urine pregnancy tests on Day 1 of each treatment cycle +/- 7 days.

¹⁴ Radiology assessment should include contrasted CT or MRI imaging of neck, chest, abdomen, and pelvis. Scans to be completed within 30 days prior to Cycle 1/Day 1.

¹⁵ Re-treatment subjects – radiology and response assessment within 14 days of Cycles 7, 14, 20, 26 then every 12 months thereafter. At the time of response assessment, bone marrow to be performed as per standard of care if other criteria for complete remission are met. CR should only be confirmed once by bone marrow assessment at planned response assessments.

¹⁶ Response Assessment to be done as per SOC to determine progression-free survival

¹⁷ For subjects being re-treated with venetoclax only. Refer to section 8.3.5.1

¹⁸ Ublituximab Cycle 3 Days 1,2, 8 & 15; Cycle 4-8 Day 1 then every 3 cycles (C11, C14, C17, C20, C23, C26). No further ublituximab after cycle 26

¹⁹ When starting retreatment, dose of umbralisib is at the investigator's discretion, previously tolerated dose should be considered.

²⁰ When starting retreatment, dose of ibrutinib or acalabrutinib is at the investigator's discretion, previously tolerated dose should be considered.

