8.2 RE-TREATMENT SUMMARY

Re-treatment Overview Cycle = 28 Days

Cohort A: Ublituximab and Umbralisib with Ibrutinib (Re-Treatment)

Cycles 1 and 2:

Ibrutinib	
Daily	
Daily at previously tolerated dose. Investigator discretion may be used to start subjects at a higher dose than last tolerated (maximum dose 420mg daily).	

Cycle 3:

Ublituximab			Ibrutinib	Umbralisib
Day 1	Day 2	Day 8 & 15	Daily	Daily
150 mg	750 mg	900 mg	At appropriate dose based on initial protocol treatment.	Previously tolerated dose. Investigator discretion may be used to start subjects at a higher dose than last tolerated (maximum dose 800mg daily).

Cycles 4 through 8:

Ublituximab	Ibrutinib	Umbralisib
Day 1	Daily	Daily
900mg	At appropriate dose based on previous Cycle	At appropriate dose based on previous Cycle

Cycles 9 through 26:

Ublituximab	Ibrutinib	Umbralisib
Day 1 of Cycle 11, 14, 17, 20, 23, 26	Daily	Daily
900 mg	At appropriate dose based on previous Cycle	At appropriate dose based on previous Cycle

Cohort B: Ublituximab and Umbralisib with Venetoclax (Re-treatment)

Cycle = 28 days

Cycle 1:

Venetoclax	
Day 1-28	
Dose escalation per package insert to previously tolerated dose. Investigator discretion may be used to escalate subjects to a target dose that is higher than the dose last tolerated (maximum dose 400mg daily).	

Cycle 2:

Venetoclax	
Day 1-7	Day 8-28
Dose escalation per package insert to previously tolerated dose, if applicable. Investigator discretion may be used to escalate subjects to a target dose that is higher than the dose last tolerated (maximum dose 400mg daily).	Tolerated dose per dose escalation

Cycle 3:

Ublituximab			Venetoclax	Umbralisib
Day 1	Day 2	Day 8 & 15	Daily	Daily
150mg	750 mg	900 mg	At appropriate dose based on previous Cycle	Previously tolerated dose. Investigator discretion may be used to start subjects at a higher dose than last tolerated (maximum dose 800mg daily).

Cycles 4 through 8:

Ublituximab	Venetoclax	Umbralisib
Day 1	Daily	Daily
900 mg	At appropriate dose based on previous Cycle	At appropriate dose based on previous Cycle

Cycles 9 through 26:

Ublituximab	Venetoclax	Umbralisib
Day 1 of Cycle 11, 14, 17, 20, 23 & 26	Daily	Daily
900 mg	At appropriate dose based on previous Cycle	At appropriate dose based on previous Cycle

Cohort C: Ublituximab and Umbralisib with Acalabrutinib (Re-Treatment)**Cycle 1-2:**

Acalabrutinib		
Every 12 hours		
previously tolerated dose		

Cycle 3:

Ublituximab			Acalabrutinib	Umbralisib

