Day 1	Day 2	Day 8 & 15	Every 12 hours	Daily

UTX-TGR-208

Version 2.0 Dated: 30 July 2020

150 mg	750 mg	900 mg	At appropriate dose based on initial protocol treatment.	Previously tolerated dose. Investigator discretion may be used to start subjects at a higher dose than last tolerated (maximum dose 800mg daily).
--------	--------	--------	--	---

Cycles 4 through 8:

Ublituximab	Umbralisib	Acalabrutinib
Day 1	Daily	Every 12 hours
900 mg	800 mg	previously tolerated dose

Cycles 9-26:

Ublituximab	Umbralisib	Acalabrutinib
Day 1 of Cycles 11, 14, 17, 20, 23 & 26	Daily	Every 12 hours
900 mg	800 mg	previously tolerated dose

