Grade ≥3	
Withhold umbralisib until Grade ≤2.
 
If recurrence after re-challenge, delay umbralisib until Grade ≤ 2; thereafter resume umbralisib at current dose or at next lower dose level at discretion of the investigator.

TABLE 4: STUDY DRUG DOSE LEVELS

Study Drug	Starting Dose	1 st Dose Reduction	2 nd Dose Reduction
Umbralisib	800 mg	600 mg	400 mg

A maximum of two dose level reductions are allowed for umbralisib. If a subject requires a dose reduction of umbralisib due to study drug related toxicity, the dose may not be re-escalated. If further evaluation of the toxicity reveals the event was not related to umbralisib, this must be recorded in the medical record and dose re-escalation to the next higher dose level may be considered at the discretion of the investigator.

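### Cohort C re-treatment tables print a fixed 800 mg of umbralisib where the rest of the protocol carries an individualised dose forward, and the synopsis version is the wrong schedule

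*Combined protocol and SAP*

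**What the plan says.** **Section 8.2, Cohort C, Cycle 3.** The umbralisib cell reads "Previously tolerated dose. Investigator discretion may be used to start subjects at a higher dose than last tolerated (maximum dose 800mg daily".

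**Section 8.2, Cohort C, Cycles 4-8 and 9-26.** Both tables give umbralisib as 800 mg daily. The Cycles 9-26 row is "Day 1 of Cycles 11, 14, 17, 20, 23 & 26 Daily Every 12 hours 900 mg 800 mg previously tolerated dose".

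**Section 8.2, Cohorts A and B, Cycles 4-8 and 9-26.** The umbralisib cells read "At appropriate dose based on previous Cycle". The synopsis uses the same wording for these two cohorts.

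**Section 7.3, footnote 19.** Not limited to any cohort: "When starting retreatment, dose of umbralisib is at the investigator's discretion, previously tolerated dose should be considered".

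**Section 8.4.2.** Table 4 has 800 mg as the starting dose, then 600 mg and 400 mg as the two permitted reductions. After a reduction for study-drug-related toxicity, "the dose may not be re-escalated". If the event proves unrelated to umbralisib, the investigator may consider going up to the next level.

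**When the triplet starts.** The synopsis text says "Umbralisib and ublituximab will be started in Cycle 3 of re-treatment". Section 5.4 agrees: "For subjects enrolled in Cohort C, retreatment will consist of 2 cycles of acalabrutinib followed by treatment with ublituximab and umbralisib", with the triplet running from Cycle 3 to Cycle 26. Yet the Cohort C table that follows in the synopsis gives all three drugs from Cycle 1, with later ublituximab on "Day 1 of Cycles 9, 12, 15, 18, 21 and 24" and umbralisib at 800 mg throughout.

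**The concern.** Re-treatment dosing is individualised at Cycle 3 in every cohort. Only Cohort C then returns to a fixed figure, and the protocol gives no reason for treating it differently. For a Cohort C subject restarting below 800 mg, one instruction says to keep the tolerated dose and another says to give 800 mg. Following the printed figure could put a subject back on a dose already reduced for toxicity.

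The synopsis table is a second and broader error. It drops the two-cycle acalabrutinib lead-in, so it affects any re-treated Cohort C subject dosed from it, whatever the umbralisib dose. Other re-treatment instructions are tied to Cycle 3: the deadline for starting pneumocystis and antiviral prophylaxis (Section 8.3.2), the ublituximab infusion rates and dilutions (Sections 8.3.1.2 and 8.3.1.3.1), and the first CMV surveillance test (Section 7.3). A site using the synopsis table would start umbralisib before any of these apply.

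This is a point about dosing clarity and safety. No comparison between cohorts is claimed to be affected.

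**Working it through.** The plan states no figure to reproduce. The check sets the umbralisib instructions for re-treatment side by side and then sizes the literal effect.

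| Re-treatment block | Cohorts A and B (Section 8.2) | Cohort C (Section 8.2) | Cohort C (synopsis table) |
|---|---|---|---|
| Cycles 1-2 | none | none | 800 mg |
| Cycle 3 | last tolerated dose, at most 800 mg | last tolerated dose, at most 800 mg | 800 mg |
| Cycles 4-8 | carried forward | 800 mg | 800 mg |
| Cycles 9 onward | carried forward, to Cycle 26 | 800 mg, to Cycle 26 | 800 mg, to Cycle 24 |

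**Cells printing 800 mg for Cohort C re-treatment.** Two in Section 8.2 (Cycles 4-8 and 9-26) and three in the synopsis (Cycle 1, Cycles 2-6 and Cycles 7-24): 2 + 3 = 5.

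**Literal step at Cycle 4 of Section 8.2, using the Table 4 dose levels.**
- From 600 mg: 800 - 600 = 200 mg; 800/600 = 1.33, or +33%.
- From 400 mg: 800 - 400 = 400 mg; 800/400 = 2.00, or +100%, which is two dose levels at once.
- From 800 mg: no change.
- Under the Cohort A and B wording the change is 0 mg in all three cases.

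**Longest possible duration.** Cycles 4 to 26 are 26 - 3 = 23 cycles; 23 x 28 = 644 days. This is an upper limit, because re-treatment also stops at confirmed U-MRD, progression or unacceptable toxicity (Section 5.4).

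**Synopsis timing.** Umbralisib starts in Cycle 1 instead of Cycle 3: 2 cycles, or 2 x 28 = 56 days early. The number of triplet cycles is the same either way (24 in Cycles 1-24; 26 - 2 = 24 in Cycles 3-26). What the table loses is the lead-in. Every maintenance ublituximab dose also falls two cycles earlier (Cycles 9 to 24 instead of 11 to 26) than the visits in the Section 7.3 schedule.

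**Interaction with Section 8.4.2.** If the earlier reduction was drug-related, neither step is allowed. If it was later judged unrelated, one level up may be considered, so 600 to 800 mg is possible at discretion but 400 to 800 mg in one step is not. In no case does Section 8.4.2 support an automatic return to 800 mg.

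**Reach.** The dose step affects only Cohort C subjects who are re-treated and restart below 800 mg. The documents do not give that number. Cohort C itself is up to approximately 28 subjects.

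**The case against.** The best defence is that 800 mg is a nominal dose. The initial-treatment tables in Section 8.1 print 800 mg for every block in all three cohorts, although Section 8.4.2 allows reductions during those cycles, and nobody reads them as sending a reduced subject back to 800 mg. On that view Section 8.4 governs and the Cohort C cells are shorthand.

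That works for initial treatment, where 800 mg is the starting dose. It does not explain a fixed figure printed straight after a Cycle 3 cell in which 800 mg is only a maximum, nor why Cohorts A and B use different words in the same place. It cannot explain the synopsis table, where the cycles themselves are wrong.

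A second objection has more force. The Cycle 3 cell in all three cohorts lets the investigator start above the last tolerated dose, up to 800 mg. The tension with the no-re-escalation rule is therefore protocol-wide, unless that rule is meant to apply only within one course of treatment. This stands, and changing the Cohort C cells alone would not resolve it. But an option left to the investigator at Cycle 3 is not the same as a scheduled 800 mg from Cycle 4.

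It is also fair that few subjects are likely to be exposed to the dose step, that a careful site would find Section 8.4.2, and that the intended lead-in is clear from the other sections. These points limit the harm but do not make the tables right.

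**Conclusion.** The point holds. Section 8.2 contradicts itself for Cohort C between Cycle 3 and Cycle 4, departs without explanation from Cohorts A and B, and conflicts with Section 8.4.2 for subjects reduced for drug-related toxicity. The synopsis Cohort C re-treatment table is the initial-treatment schedule in the wrong place.

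The size is a literal increase of 33% or 100% at Cycle 4, lasting at most 644 days, and an umbralisib start 56 days early in the synopsis. This rests on reading the printed cells as written and on the Table 4 dose levels. How many subjects would meet the dose step cannot be worked out from the documents.

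This is an internal inconsistency rather than a design decision. It should be corrected because it sits in dosing tables and could affect subject safety, although Section 8.4.2 offers partial protection.

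**What to change.** 1. In Section 8.2, Cohort C, Cycles 4-8 and 9-26, replace the umbralisib 800 mg with the Cohort A and B wording, "At appropriate dose based on previous Cycle", adding a maximum of 800 mg daily and a reference to Section 8.4.2.
2. Replace the Cohort C re-treatment table in the synopsis with the corrected Section 8.2 schedule: acalabrutinib alone in Cycles 1-2, the triplet in Cycles 3-26, and umbralisib restarted at the last tolerated dose in Cycle 3 and carried forward.
3. In the same amendment, state for all cohorts whether the ban on re-escalation in Section 8.4.2 carries over from initial treatment into re-treatment, so that the Cycle 3 discretion and that rule can be read together.
4. Until then, send sites a short clarification.

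The cost is two cells, one synopsis table and one clarifying sentence at the next amendment. Sample size, endpoints and analysis are unchanged.

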8.3 AGENT ADMINISTRATION

Ublituximab treatment will be administered as an IV infusion. Umbralisib, ibrutinib, acalabrutinib and venetoclax will be self-administered orally. Ublituximab, umbralisib, ibrutinib and acalabrutinib will be administered on an outpatient basis. Venetoclax can be administered on an inpatient or outpatient basis as guided by the package insert.

8.3.1 GUIDELINES FOR ADMINISTRATION OF UBLITUXIMAB

- *Method of Administration:* Ublituximab will be administered as an intravenous infusion through a dedicated line.
- *Potential Drug Interactions:* No drug interactions have been reported to date.
- Pre-medications should include an antihistamine (diphenhydramine 50 mg or equivalent), and a corticosteroid (dexamethasone 10-20mg or equivalent).
 - If administered IV: start ublituximab 30 minutes after conclusion of last pre-med infusion.
 - If administered orally: start ublituximab 45-60 minutes after ingestion of pre-meds.
 - If subject does not tolerate pre-medications, or pre-medications have an adverse impact on coexisting medical conditions consider changing the pre-medication dosage, change to a different drug or discontinue at the investigator's discretion
 - Corticosteroids premeds can be stopped after Cycle 6 if subject is tolerating infusion without infusion related reactions.

- Use of oral acetaminophen 650 mg (or equivalent) should be restricted to subjects who experience fever or pyrexia after week 1 dose, or as clinically warranted.
- *Hypersensitivity and Infusion Reaction Precautions:* Medication and resuscitation equipment must be available per institutional guidelines prior to ublituximab administration for the emergency management of potential anaphylactic reactions.
- *Subject Care Implications:*
 - Ublituximab should not be administered as an IV push or bolus.
 - Diluted ublituximab should be checked before administration for cloudiness, color, or deposits. Ublituximab should not be administered if does not conform to the specifications. Immediately inform the Monitor/Sponsor with any product quality concerns or questions.
 - It is recommended that ublituximab be administered immediately after dilution.
 - No other treatment may be co-administered with ublituximab (other than for immediate intervention for adverse event).
 - Corticosteroid therapy started at least 7 days prior to Cycle 1/Day 1 (prednisone \leq 10 mg daily or equivalent) is allowed as clinically warranted. Topical or inhaled corticosteroids are permitted
 - Since infusion-related hypotension may occur, investigator should consider holding antihypertensive medications approximately 12-24 hours prior to and throughout infusion of ublituximab. Decision to withhold antihypertensive medication is at investigator discretion.
 - For subjects at risk for tumor lysis syndrome in the opinion of the treating investigator, prophylaxis with allopurinol or per recommended institutional standards should be considered.

